## **3.5. Adverse and Serious Adverse Events**

### **3.5.1. Definition of Adverse Events**

An AE is any untoward medical occurrence in a patient or clinical study subject administered a study medication (pharmaceutical/biological product) that does not necessarily have a causal relationship to this medication. An AE can, therefore, be any unfavorable and unintended sign (including abnormal laboratory findings), symptom, or disease temporally associated with the use of the study medication, whether or not related to the study medication. Study medication includes the investigational drug under evaluation and the comparator product or vehicle placebo that is given during any phase of the study.

Medical conditions/diseases present before signing the informed consent form are only considered AEs if they worsen after the informed consent form is signed. Abnormal test results constitute AEs only if they induce clinical signs or symptoms, are considered clinically significant, or require additional therapy or a change in therapy.

At each study visit the subject will be asked how he/she has been feeling. All AEs whether observed by the Investigator or spontaneously reported by the subject will be documented in the subject's chart and the AE eCRF.

Adverse events also may be detected when they are volunteered by the subject between visits or through study assessments.

### **3.5.2. Serious Adverse Event**

A serious adverse event (SAE) is any untoward medical occurrence that at any dose:

- Results in death,
- Is life-threatening,

Note: The term "life-threatening" refers to an event in which the subject was at risk of death at the time of the event; it does not refer to an event which hypothetically might have caused death if it were more severe.

- Results in persistent or significant disability/incapacity (excluding progression/outcome of the disease under study),
- Is a congenital anomaly/birth defect,
- Requires inpatient hospitalization or prolongation of existing hospitalization, or
- Is medically significant; i.e., defined as an event that jeopardizes the health of the subject or may require medical or surgical intervention to prevent one of the outcomes listed above.

Treatment on an outpatient emergency basis that does not result in hospital admission with an overnight stay is not considered an SAE.

All SAEs that are ongoing at the time of completion or discontinuation from the study will be followed until stabilization or resolution of the event.

### 3.5.3. Relationship to Study Medication

The relationship of AEs to the study medication should be assessed by the Investigator using the definitions below.

**Not suspected:** The temporal relationship of the event to the study medication makes a causal relationship unlikely, or, other drugs, therapeutic interventions or underlying conditions provide a sufficient explanation for the observed event.

**Suspected:** The temporal relationship of the event to the study medication makes a causal relationship possible or other drugs, therapeutic interventions or underlying conditions do not provide a sufficient explanation for the observed event.

If there is any valid reason, even if undetermined, for suspecting a possible cause-and-effect relationship between the study medication and the occurrence of the AE, then the AE should be considered "suspected."

If the relationship between the AE/SAE and the study medication is determined by the Sponsor to be "suspected," the event will be considered to be related to the study medication for the purposes of expedited regulatory reporting.

### 3.5.4. Recording Adverse Events

Adverse events spontaneously reported by the subject and/or in response to an open-ended question from the study personnel or revealed by observation, regardless of severity or potential association with the study medication or study procedures, will be recorded in the eCRF. All AEs that occur after a subject has signed the informed consent form until the final study visit should be collected and recorded on the AE eCRF page. Adverse events will be followed until the event is resolved or stabilized, and SAEs that

are ongoing at the time of completion or discontinuation from the study will be followed until resolution.

The AE term should be reported in standard medical terminology when possible. For each AE, the Investigator will evaluate and report the following:

- Onset (date);
- Resolution (date);
- Severity grade (mild, moderate, severe);
- Relationship to study medication (not suspected, suspected);
- Action taken (none, study medication temporarily interrupted, study medication permanently discontinued, concomitant medication taken, hospitalization/prolonged hospitalization, other);
- Serious outcome (yes/no).

The severity grade should be determined by the Investigator using the definitions below:

- **Mild:** Discomfort noticed but no disruption of normal daily activity
- **Moderate:** Discomfort sufficient to cause interference with normal daily activity
- **Severe:** Incapacitating, with inability to perform normal activities

#### **4. SAMPLE SIZE AND POWER CONSIDERATIONS**

In accordance with the International Council for Harmonisation (ICH) E1A Guidance, safety data for a minimum of 100 subjects treated for one year is recommended for inclusion in applications for marketing approval. The masking of subject treatment assignments in Study OTX-101-2016-001 will be maintained until the database for that study has been locked, so qualified subjects receiving OTX-101 0.09% or vehicle may be enrolled in Study OTX-101-2016-002. Approximately 300 subjects will enroll in Study OTX-101-2016-002 of which it is anticipated that at least 150 will have been randomly assigned to OTX-101 0.09% in Study OTX-101-2016-001.

## **5. ANALYSIS POPULATIONS**

Three populations will be used for analysis.

### **5.1. Safety Analysis Populations**

The safety population will include all patients who were enrolled in Study OTX-101-2016-002 and received at least one dose of the study medication.

Summaries will be presented by the following groups of subjects:

1. subjects assigned to the OTX-101 0.09% arm in Study OTX-101-2016-001; i.e., those subjects with 12 months exposure to active drug.
2. subjects assigned to the Vehicle arm in Study OTX-101-2016-001; i.e., those subjects with at least 9 months of exposure to active drug.

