
Methodology: This is an open-label extension of OTX-101-2016-001, a randomized, multicenter, double-masked, vehicle-controlled study in which subjects were randomized to 1 of 2 treatment arms and treated for 12 weeks as follows:
 
 • OTX-101 0.09% (N = ■■■ subjects) • Vehicle (N = ■■■ subjects) 
Subjects successfully completing Study OTX-101-2016-001 may be eligible to enroll in this 40 to 52 week open label extension study in which all subjects will receive OTX-101 0.09% therapy. Subjects may also use unpreserved artificial tears, as needed. Subjects assigned to OTX-101 0.09% in Study OTX-101-2016-001 will participate for 40 weeks. Subjects assigned to vehicle in Study OTX-101-2016-001 are eligible to participate for 52 weeks. Both subject sets will total 52 weeks of participation receiving OTX-101 0.09%.
 
Subjects may enroll in Study OTX-101-2016-002 for up to 14 days following completion of Visit 5 of Study OTX-101-2016-001. At Visit 5a, sites will obtain signed informed consent and dispense study medication. If Visit 5a is not conducted on the same day as Visit 5 of Study OTX-101-2016-001, any female subject of childbearing potential must also have a negative urine pregnancy test. Study “Day” approximately reflects the cumulative number of days of exposure to study drug since the baseline visit of Protocol OTX-101-2016-001, regardless of actual calendar time elapsed.
 
Subjects will self-administer study medication topically to both eyes BID for 40 to 52 weeks depending on their treatment assignment in Study OTX-101-2016-001. Safety evaluations for all subjects will be conducted at study visits on Days 182, 273 and 364; the window for Visits 6 (Day 182) and Visit 7 (Day 273) will be ± 7 days; the window for Visit 8 (Day 364) will be +14 days for those subjects assigned to OTX-101 0.09% in Study OTX-101-2016-001. (± 14 days for subjects assigned to vehicle in Study OTX-101-2016-001, participating for 52 weeks in Study OTX-101-2016-002). Subjects assigned to vehicle in Study OTX-101-2016-001, participating for 52 weeks in Study OTX-101-2016-002, will also be evaluated at Visit 9 (Day 448), which will have a visit window of +14 days. Both eyes will be assessed at each visit. Adverse events and concomitant medications will be documented from signing of informed consent to the subject’s final visit.
	

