11.5. Analysis Populations

Two populations will be used for analysis.

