11.5.1.1. One Year Safety Population

Certain analyses will include only those subjects with a total of 1 year of exposure to active drug in Studies OTX-101-2016-001 and OTX-101-2016-002. The combined safety data from both protocols will be analyzed for this population.

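### The SAP drops the protocol's One Year Safety Population and its combined-study data without declaring it, so no adverse-event table covers a full active year in a defined one-year group

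*SAP*

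**What the plan says.** Protocol 11.5 states "Two populations will be used for analysis". One is the safety population. The other, the One Year Safety Population, is set out in 11.5.1.1: "Certain analyses will include only those subjects with a total of 1 year of exposure to active drug in Studies OTX-101-2016-001 and OTX-101-2016-002". It adds: "The combined safety data from both protocols will be analyzed for this population". Membership depends on exposure, not on the Study 001 arm. The synopsis fits this: "Subjects assigned to vehicle in Study OTX-101-2016-001 are eligible to participate for 52 weeks", so that both origins are meant to reach 52 weeks on active drug. Protocol 11.8 merges the Study 001 safety data for everyone enrolled and summarises adverse events from Day 0 of Study 001 to the Day 364 or Day 448 visit.

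SAP 5 states "Three populations will be used for analysis". SAP 5.1 then defines one, the safety population, for which a single dose is enough, and reports it in two groups set by Study 001 arm. The OTX-101 group is glossed as "those subjects with 12 months exposure to active drug" and the other group is "subjects assigned to the Vehicle arm in Study OTX-101-2016-001; i.e., those subjects with at least 9 months of exposure to active drug".

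Elsewhere in the SAP:
- 7.6 starts treatment-emergent adverse events (TEAEs) at the first OTX-101 dose in Study 002, plus earlier events that worsen afterwards.
- 7.7 and 7.8 tabulate extension visits and baseline only; 7.9 and 7.10 tabulate extension visits only.
- 7.5 counts subjects by duration of exposure, with a top category of 12 months or more (360 days).
- 10 names the Safety Population on every table that names a population.
- 8 reports no changes from the protocol.

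**The concern.** Long-term safety is the study's only objective, and the only sample-size argument (Protocol 11.4, SAP 4) is the ICH E1A recommendation of one-year data in 100 or more subjects. The vehicle-origin subjects are offered 12 further weeks so that they too can reach a year on drug. One would expect the SAP to show what happened to people who had a year of OTX-101, over that whole year. Grouping by Study 001 arm does not do this, because assignment is not exposure. Starting TEAEs in Study 002 does not do it either, because part of the active year lies in Study 001. With SAP 8 silent, a reader of the report would not know that a protocol analysis had been left out.

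**Working it through.** **The plan's own figure.** SAP 4 expects about 300 subjects, at least 150 of them from the OTX-101 arm. With the 1:1 allocation in Protocol 11.1, 300 × 1/2 = 150, so the figure reproduces. There is no power calculation to check.

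**Days on drug and days counted.** Inputs are the nominal visit days: 84 (Visit 5/5a), 364 (Visit 8) and 448 (Visit 9).

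| Subject | On OTX-101 in Study 001 | On OTX-101 in Study 002 | Total | TEAE counting under SAP 7.6 | SAP 5.1 label |
|---|---|---|---|---|---|
| OTX-101 origin, completes Visit 8 | 84 | 364 − 84 = 280 | 364 | 280 | 12 months |
| Vehicle origin, completes Visit 9 | 0 | 448 − 84 = 364 | 364 | 364 | at least 9 months |
| Vehicle origin, stops at Visit 8 | 0 | 364 − 84 = 280 | 280 | 280 | at least 9 months |
| Either origin, stops well before Visit 8 | 84 or 0 | under 280 | below the label | Study 002 days only | same as its arm |

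Four things follow.

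1. The first two rows have the same exposure, 364 days or 52 weeks. Both meet the protocol's one-year criterion and the 360-day cut in SAP 7.5, but they sit in different groups, each mixed with subjects who do not meet it. Neither group, nor the two together, is the protocol's one-year population.
2. The exposure labels are untrue for early stoppers in both groups, since one dose is enough to be included.
3. For an OTX-101-origin completer, 364 − 280 = 84 days on drug, or 84/364 = 23%, lie outside TEAE counting. An event that began then and did not worsen later appears in no TEAE table of this study.
4. The only subjects whose full active year is counted are the vehicle-origin Visit 9 completers, and no column isolates them.

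**What remains.** The exposure table in SAP 7.5 still counts subjects at 360 days or more. It takes the last dosing date minus the first, plus one, but does not say in which study the first date lies. If the clock starts at Visit 5a, an OTX-101-origin completer reaches about 280 days, or 280 + 14 = 294 at the end of the Visit 8 window. Both are below 360, so nobody treated on schedule in that arm could enter the category. If it starts at Day 0 of Study 001, the same subject has 364 days and does enter.

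**The SAP's own practice.** SAP 7 sets baseline at the first OTX-101 dose in either study, so an OTX-101-origin subject has a Day 0 baseline but a TEAE start at about Day 84. SAP 9 selects its interim subset of 165 subjects by total exposure across the two studies. A combined-exposure population is therefore within reach of the existing data.

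**The case against.** Several points on the other side stand, at least in part.

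- The label 'at least 9 months' literally includes 12 months, so it is not false for vehicle-origin subjects who complete 52 weeks. The fault there is that they are not separated.
- The 100-subject recommendation is a count, and SAP 7.5 does count subjects at 12 months or more. But that table carries no safety outcome, and its starting dose is undefined.
- The protocol speaks only of certain analyses and names no tables. How many outputs to produce is open; producing none is not consistent with it.
- 'Three' may mean the safety population plus its two groups. That would explain the number but still leave the one-year population out.

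A reader might go further and infer that one-year evidence shrinks to the OTX-101-origin half (258/2 = 129 of the 258 enrolled, if they split equally), with a matching fall in the chance of seeing a rare event. The documents do not support this. Every dosed subject of either origin is in the Safety Population, and the schedule and SAP 3.5.4 run event collection to the final visit, so no vehicle-origin event leaves the tables. Nor does the OTX-101-origin group supply a full counted year, as the table shows. (SAP 2.2 says events are documented to Day 364; that needs aligning with the schedule, which governs collection.)

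A reader might also infer that the target of 100 will be missed. With 129 in the OTX-101-origin group, more than 1 − 100/129 = 22% would have to be lost, and the documents give no retention rate.

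**Conclusion.** The concern holds as an undeclared omission. The SAP leaves out the One Year Safety Population of Protocol 11.5.1.1 and, for adverse events, the merged Study 001 data of Protocol 11.8. As a result no adverse-event table reports a full active year in a defined one-year group.

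For each OTX-101-origin completer, 84 of 364 active days (23%) fall outside TEAE counting. For vehicle-origin subjects, 364-day and 280-day exposures are reported together. The missing denominator cannot be fixed from the documents. If 60% to 90% of the 258 enrolled reached a year in both origins (an assumption), it would be 0.6 × 258 = 155 to 0.9 × 258 = 232 subjects. That range may flatter the vehicle origin, where the extra 12 weeks are optional. It describes a group that the plan fails to isolate, not events that it fails to report.

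The day counts assume nominal visit days and uninterrupted dosing.

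**What to change.** In the SAP:

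1. **Section 5.** Correct 'Three', delete the two exposure glosses in 5.1, and describe those groups by Study 001 arm only. Define the One Year Safety Population by actual days on OTX-101 across both studies, whatever the origin.
2. **Threshold.** Use one figure for a year throughout, reconciling 52 weeks (364 days) with the 360-day cut in 7.5; a completer at the nominal visit days meets either. State whether a gap of up to 14 days between Visit 5 and Visit 5a counts, because last date minus first date plus one would include it.
3. **Section 7.6.** For this population, count TEAEs from the first OTX-101 dose in either study, on merged data. A one-year column built on the present TEAE start would still omit new events from the first 84 days on drug in the OTX-101-origin subjects.
4. **Section 7.5.** Start the exposure clock at that same dose.
5. **Section 10.** Name at least the adverse-event summary tables that use the population, and show it beside the full Safety Population. Subjects who reach a year are selected for having stayed on drug, so early stoppers must remain visible.
6. **Section 8.** List what still departs from Protocol 11.5 and 11.8. One such item is that counting from the first OTX-101 dose leaves out vehicle-origin events during the Study 001 vehicle period, which the Day 0 start in 11.8 would include.

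The cost is SAP wording, one further set of adverse-event outputs, and a data merge that the protocol already plans. No new data are collected.

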**6. HANDLING OF MISSING DATA**

No missing data will be imputed. The reasons for missing data will be recorded.

## 7. STATISTICAL ANALYSIS

All statistical analyses and reporting will be performed using the SAS® System Version 9.3 or later.

Unless otherwise specified, continuous variables will be summarized with descriptive statistics (n, mean, median, standard deviation, standard error, minimum, and maximum), and categorical variables will be summarized with counts and percentages.

### **Definition of Baseline:**

Baseline measurements will be the last measurement for the corresponding variable prior to the first dose of OTX-101 0.09%. For those initially randomized to OTX-101 0.09%, baseline would be the day of randomization (Day 0). For those initially randomized to Vehicle, baseline would be the day of the first dose of OTX-101 0.09% in the extension phase.

### **Out of Window and Unscheduled Visits:**

Data will be presented according to the assigned visit in the database.

### **7.1. Subject Disposition**

Subject disposition, including the number of subjects entering the extension phase and completing the extension phase will be tabulated. The percentage of subjects treated and completing the study will be based on the total number entering the extension phase. A subject data listing will be provided.

The total number and percentage of subjects included in each of the analysis datasets will be summarized with percentages based on the total number of subjects entering the extension phase. A subject data listing will be provided.

Discontinuations and the reasons for discontinuation from the study will be summarized for all subjects. Summaries will include the number and percentage of subjects. Reasons for discontinuation following the receipt of study drug will include the following:

- Withdrawal by Subject
- Lost to Follow-up
- Adverse Event
- Pregnancy
- Death
- Physician Decision
- Protocol Deviation
- Other

A subject data listing will be provided.

## **7.2. Demographic and Baseline Characteristics**

Subject demographic and baseline characteristics will be summarized for the safety population. Summary tables will be supported with individual subject data listings.

Continuous variables such as age will be summarized using descriptive statistics (n, mean, standard deviation, median, minimum, and maximum), and categorical variables such as gender, race, ethnicity, and iris color will be summarized using counts and percentages of subjects.

Age will be determined as the whole integer number of years from the date of birth (DOB) to the date of the screening visit, i.e., the truncated integer difference between the DOB and Visit 1.

## **7.3. Concomitant Medications**

A subject data listing will be provided. Medications used prior to the first dose of OTX-101 0.09%, but stopped prior to first dose will be indicated separately from those used concomitantly with OTX-101 0.09% on the listing.

## **7.4. Ocular and Other Medical History**

A subject data listing will be provided.

## **7.5. Treatment Compliance and Exposure**

The % compliance on OTX-101 0.9% will be summarized over all visits by the categories of <70% and  $\geq$ 70%.

Duration of drug exposure will be calculated for each subject as the last date of dosing minus the first date of dosing + 1. The number and percentage of subjects will be summarized according to the following duration-of-exposure categories: '< 3 mon (90 days)', '3 to < 6 mon', '6 mon to < 9 mon', '9 to < 12 mon', and ' $\geq$ 12 mon (360 days)'. A subject data listing will be provided.

## **7.6. Adverse Events**

A treatment-emergent adverse event (TEAE) is one that was experienced on or after the day of first dose of OTX-101 0.09% in Study OTX-101-2016-002; or if experienced prior to first dose, worsened after first dose.

An overall summary will be presented which gives the number and percentage of subjects within each cohort that experienced a TEAE, experienced any treatment-related TEAE, permanently discontinued treatment due to a TEAE, experienced a treatment emergent SAE, and that died.

In summary tables, AEs occurring in both eyes will be summarized once at the greater intensity and relationship to study drug.

Events that are possibly or probably related will be counted as an event related to study drug.

The number and percentage of subjects experiencing one or more events within a Medical Dictionary for Regulatory Activities (MedDRA) System Organ Class (SOC) and Preferred Term (PT) class without regard to intensity, relationship, or seriousness will be tabulated by cohort. In addition, tables will display events by SOC, PT, and maximum intensity or closest relationship to treatment.

The number of deaths and SAEs will also be presented, and AEs leading to premature discontinuation from the study will be listed and tabulated.

A glossary listing that shows the verbatim terms assigned to each SOC and PT will be provided.

A listing of TEAEs by cohort ordered by subject, SOC, PT, and onset date will be provided.

A listing of serious TEAEs by cohort ordered by subject, SOC, PT, and onset date will be provided.

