11.8. Safety Analyses

Safety and tolerability data will be presented in tables of descriptive statistics and frequency distribution. All summary tables will be supported with individual subject data listings. For all subjects enrolled in Study OTX-101-2016-002, the safety data recorded during Study OTX-101-2016-001 will be merged to produce a dataset encompassing one year of exposure to treatment.

AEs that occurred during the run-in period on vehicle of Protocol OTX-101-2016-001 will be summarized separately from AEs that occur from the first dose of double-masked treatment on Day 0 of that protocol to the Day 364 or Day 448 visit of Protocol OTX-101-2016-002.

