### **2.2. Study Design**

This will be an extension of OTX-101-2016-001, a randomized, multicenter, double-masked, vehicle-controlled study that enrolled male and female subjects, 18 years of age and older, with a patient-reported history of KCS for a period of at least 6 months, a clinical diagnosis of bilateral KCS supported by OTX-101-2016-001 study assessments, and corrected Snellen visual acuity (VA) of better than 20/200 in both eyes at Screening and at Baseline.

Subjects who complete Visit 5 (Day 84) of Study OTX-101-2016-001 may be eligible to enroll in protocol OTX-101-2016-002 within 14 days at the discretion of the Principal Investigator and Sponsor. Subjects who provide written informed consent at Visit 5a and meet the inclusion/exclusion criteria requirements will be enrolled in the study and receive study medication (OTX-101 0.09%). All subjects will participate for at least 40 weeks. Subjects who were randomized to the vehicle arm in Study OTX-101-2016-001 may have the opportunity to participate for an additional 12 weeks, and a total of 52 weeks.

Subjects will self-administer study medication topically to both eyes twice daily (BID) from Visit 5a to Visit 8 (Day 364) or Visit 9 (Day 448). Safety evaluations will be conducted at all study visits. The window for Visits 6 and 7 will be  $\pm 7$  days. The window for Visit 8 will be +14 days for those subjects assigned to OTX-101 0.09% in Study OTX-101-2016-001 ( $\pm 14$  days for subjects assigned to vehicle in Study OTX-101-2016-001, participating for 52 weeks in Study OTX-101-2016-002), and for Visit 9 the window will be +14 days. Both eyes will be assessed at each visit. Adverse events (AEs) and concomitant medications will be documented at each study visit from signing of informed consent to Day 364.

A total of approximately 700 subjects will be enrolled in Protocol OTX-101-2016-001 (approximately 350 subjects in each treatment arm) at approximately 50 clinical sites. Subjects who successfully complete that study may be eligible to participate at the discretion of the Principal Investigator and the Sponsor with the goal of enrolling approximately 300 subjects in Protocol OTX-101-2016-002.

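### The SAP counts treatment-emergent AEs only from the first Study 002 dose, so the cohort labelled as having 12 months on drug loses its first 84 on-drug days from the planned AE tables

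*SAP*

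**What the plan says.** SAP 7.6 applies one TEAE definition to both cohorts: an event "experienced on or after the day of first dose of OTX-101 0.09% in Study OTX-101-2016-002", or an earlier one that worsened after first dose. In SAP 10, AE tables 14.3.1.1 to 14.3.1.6, the serious-event listing 14.3.2 and Listing 16.2.7 are all titled as treatment-emergent. No all-AE table or listing is planned.

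SAP 5.1 splits the safety population by Study 001 arm. It describes the OTX-101-origin group as "those subjects with 12 months exposure to active drug" and the vehicle-origin group as "those subjects with at least 9 months of exposure to active drug". SAP 5 opens with "Three populations will be used for analysis" but goes on to define only the safety population, with these two subgroups.

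The protocol sets a different plan. Under section 11.8, for everyone enrolled in Study 002, "the safety data recorded during Study OTX-101-2016-001 will be merged to produce a dataset encompassing one year of exposure to treatment". The same section keeps run-in events on vehicle apart from "AEs that occur from the first dose of double-masked treatment on Day 0 of that protocol to the Day 364 or Day 448 visit". Section 11.5.1.1 sets up a One Year Safety Population of subjects with a year on active drug across the two studies: "The combined safety data from both protocols will be analyzed for this population".

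SAP 8 states that nothing has changed from the protocol.

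**The concern.** An OTX-101-origin subject's first exposure to the drug is in Study 001. If an AE began then and did not worsen after the first Study 002 dose, it is not a TEAE under SAP 7.6. It stays in the Study 001 database but does not reach this study's AE tables or Listing 16.2.7. The label on that cohort nevertheless claims a full year, so a reader would naturally take the AE percentages as one-year incidence.

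Two things follow. First, subjects are counted once per term over a fixed denominator, so dropping a period can only lower or leave unchanged the overall and per-term percentages. Second, the by-cohort columns do not cover the same stretch of treatment. The OTX-101-origin column covers drug weeks 12 to 52. The vehicle-origin column covers drug weeks 0 to 40, or 0 to 52 for those who extend (SAP 2.2 says they "may have the opportunity to participate for an additional 12 weeks"). Early-onset events are therefore counted in one column only.

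Long-term safety is the only objective and AE incidence is the main result, so this affects the core of the report.

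**Working it through.** No power or sample-size formula applies. The check is day arithmetic plus a comparison of sections.

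**1. Reproduce the plan's own clock** (Schedule of Procedures; protocol synopsis).
- Study 001 treatment: 12 × 7 = 84 days. Study 002, OTX-101-origin: 40 × 7 = 280 days. 84 + 280 = 364 = 52 × 7, which is Visit 8.
- The legible schedule pairs agree: 84 + 98, 143, 189, 234, 280 and 325 give Days 182, 227, 273, 318, 364 and 409.

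**2. On-drug time outside the TEAE window.**
- OTX-101-origin: 84/364 = 23.1%. If Visit 8 falls at the end of its +14-day window, 84/378 = 22.2%.
- Vehicle-origin: 0 days, because their first OTX-101 dose is in Study 002. Their Study 002 dosing is 280 days to Visit 8 or 448 − 84 = 364 days to Visit 9.
- For 150 OTX-101-origin subjects (the minimum anticipated in SAP 4), the excluded time is 150 × 84 = 12,600 of 150 × 364 = 54,600 person-days.

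**3. Can the 12-month label hold on Study 002 dosing alone?**
- Longest Study 002 dosing by the SAP 7.5 formula: 280 + 14 + 1 = 295 days.
- Supply before Visit 8 (protocol 8.5.1): 3 boxes × 105 days = 315 days.
- Both fall short of the 360 days that SAP 7.5 sets for its top exposure category. The label is true only if Study 001 dosing is counted. Exposure and AE counts would then cover different periods.

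**4. The sections side by side.**

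| Item | Start point, OTX-101-origin cohort |
|---|---|
| Protocol 11.8, AE summary | Day 0 of Study 001 |
| Protocol 11.5.1.1, one-year analysis | Both studies combined |
| SAP 7, baseline for VA and IOP | Day 0 of Study 001 |
| SAP 5.1, cohort label | Implies Study 001 dosing is counted |
| SAP 7.5, exposure | Study of the first dose not stated |
| SAP 7.6, TEAE | First Study 002 dose |

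Only the TEAE rule starts explicitly in Study 002.

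**5. Illustration of size, not a bound.** Protocol 4.4 gives 12-week Phase 2b rates at 0.09%: 15.1% instillation site pain and 19.7% related AEs. The OTX-101-origin number is taken as 129 (assumed half of the 258 enrolled, SAP 9) or 150 (SAP 4).

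| Subjects | Instillation site pain | Related AE |
|---|---|---|
| 129 | 129 × 0.151 = 19.5 | 129 × 0.197 = 25.4 |
| 150 | 150 × 0.151 = 22.7 | 150 × 0.197 = 29.6 |

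If half of these subjects had the event again or worse in Study 002 (assumed), they would still be counted. About 10 to 11 subjects with pain and 13 to 15 with related AEs would then be missing from the tables. The full counts in the table are probably too high, because only Study 001 completers enrol and recurrent events still count.

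**The case against.** The best defence is that the SAP means to report the extension only. Section 7.6 names Study 002 openly. Sections 7.7 to 7.10 also restrict VA, IOP, slit lamp and fundus results to extension visits, plus baseline for the first two. No table is titled one-year incidence, and the 12-month wording may describe cumulative exposure rather than an AE window. That reading is fair, but the scope is not declared in SAP 8 and leaves the analyses promised in protocol 11.5.1.1 and 11.8 undone.

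Several narrower points stand:
- Entry requires completing Study 001, so the death count is unaffected and table 14.3.1.5 (withdrawals) nearly so. Table 14.3.1.6 is a glossary. The gap lies in the any-TEAE, related, SOC/PT, intensity and relationship counts, and in serious events after which the subject still completed Study 001.
- The SAP 7.6 sentence on deaths and SAEs, and the narratives (14.3.3), carry no explicit TEAE limit. Neither would show routine early AEs.
- The definition speaks of events experienced, not starting, after first dose, so an ongoing Study 001 event might be read as included. The separate clause on worsening argues against that. SAP exclusion 1 also bars unresolved Study 001 AEs, although the protocol's version leaves this to judgement.
- SAP 9 reports that safety data for 165 subjects, selected on combined exposure, went into the NDA. That was an interim cut at 12 May 2017 and does not supply this study's one-year tables.
- The Phase 2b counts rest on assumptions. Only 84/364 comes from the documents.

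**Conclusion.** The concern holds. Following SAP 7.6 as written leaves 84 of 364 nominal on-drug days (23%) outside AE reporting for the OTX-101-origin cohort. This conflicts with protocol 11.8 and 11.5.1.1, and SAP 8 does not disclose it. The effect runs one way: the planned tables, read as that cohort's year on drug, understate AE incidence or at best leave it unchanged. The number of subjects affected cannot be known from the documents.

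The conclusion does not depend on the Phase 2b illustration. It rests on the nominal visit schedule and on reading the worsening clause as the only route by which an earlier event counts. Read literally, protocol 11.8 also brings in vehicle-period AEs of vehicle-origin subjects. SAP 7.6 leaves those out too, but they are not on-drug events and are not part of the 23%.

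This must be fixed before the analysis is run, because of the undeclared conflict with the protocol on the study's main outcome.

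**What to change.** - **SAP 7.6:** define a TEAE as an AE with onset or worsening on or after the first dose of OTX-101 0.09% in either study, through the subject's final visit. Merge Study 001 AE records for OTX-101-origin subjects.
- **SAP 5 and 10:** define the One Year Safety Population, correct the count of populations, and add the combined-data AE tables and listing.
- **SAP 7.5:** state that exposure starts at the first OTX-101 dose in either study, so exposure and TEAEs share one window.
- **SAP 8:** show Study 001 vehicle-period AEs of vehicle-origin subjects separately, and record this as a departure from the literal wording of protocol 11.8.
- **Useful but optional:** label each column with its on-drug window and give total subject-days at risk, since vehicle-origin subjects who stop at week 40 have shorter follow-up even after the fix. A Study 002-only TEAE table can stay as supplementary.

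The cost is SAP wording, one population definition, some programming and a merge of existing records; no new data are needed. One item to check is causality coding. SAP 7.6 counts possibly or probably related events, whereas Study 002 records suspected or not suspected, and the documents do not show the Study 001 scale, so the merge may need harmonising. Overall and per-term AE percentages for the OTX-101-origin cohort can only stay the same or rise.
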